4. TREATMENT AND DEVICE

The intervention involves the use of VERASENSE by the surgeon during Total Knee Replacement Surgery. VERASENSE is available for use with the Stryker Triathlon Total Knee System. VERASENSE replaces the standard tibial trial inserts and is embedded with microelectronics and sensors to provide surgeons with real-time knee kinetic data. The data is wirelessly transmitted to a graphic display (VERASENSE Knee Application), allowing surgeons to quantify and assess soft tissue intercompartmental loads throughout the range of motion. The VERASENSE sensor is not an investigational device. OrthoSensor, Inc., received FDA 510K clearance in 2009. The indication for use is a tool for adjustment of the femoral knee

implant to reduce instability from flexion gap asymmetry. The VERASENSE sensor is sterile and single patient use.

4.1 – Description of VERASENSE

- One articulation (Figure 1): Cruciate Retaining (CR); However can be utilized with Posterior stabilizing implant designs
- Six Sizes: 2, 3, 4, 5, 6, 7
- Four attachable shim thicknesses: 9, 11, 13, and 16mm

[figure not shown]
Figure 1 – CR VERASENSE Inserts

4.2 – VERASENSE Knee Application (Figure 2)

- Graphic display is a 27" iMac with keyboard, mouse, bar-code reader, activation magnet, receiver (Antenna)
- Software application provides femoral contact point location and load values for medial and lateral condyles; kinematic tracking; tray rotation, tibia varus/valgus axis; mechanical axis

Figure 2 – Graphic Display

5. METHODS / PROCEDURES

Patients indicated for TKA and who meet all study eligibility criteria will be asked to participate in the study. Eligible patients will receive a primary unilateral PCL-retaining or – sacrificing TKA using the Stryker Triathlon Total Knee System *with* or *without* the use of the VERASENSE™ Knee System. Patients will be enrolled in a consecutive series consisting of two cohorts (Groups A and B). Both groups are described below:

Group A – Control (Surgeon-Guided) will consist of **250** consecutive patients who will undergo primary unilateral PCL-retaining or – sacrificing TKA using the Stryker Triathlon Total Knee System *without* the use of VERASENSE to guide rotational alignment and balance. **Prior to closing the arthrotomy, VERASENSE will be utilized in a surgeon-blinded fashion to record rotational alignment and intercompartmental pressures through a range of motion.**

Group B (Sensor-Guided) will consist of **250** consecutive patients who will undergo primary unilateral PCL-retaining or – sacrificing TKA using the Stryker Triathlon Total Knee System *with* the use of VERASENSE to guide rotational alignment and balance. The sensor data will be used for balancing per the VERASENSE protocol below.

Each patient will be given a unique study number once informed consent has been obtained. The investigator will be blinded to the patient study number and the patient will be blinded to his/her assigned group. It will be important that all patients remain blinded to their assigned group. The patient will be informed during the consent process that they may or may not receive their knee replacement procedure using the VERASENSE Knee System.

Radiographic outcomes will be assessed on all patients within the first 12 weeks and at the annual visits. Any postop complications will also be monitored.

Surgical Protocol – Using VERASENSE

All knees will be prepared using standard instrumentation and a measured resection or gap balancing technique. The following steps will be performed when using VERASENSE:

Step 1: Establish Tibial Tray Rotation:

Select and position appropriate sized trial tibial tray. Align the tray to the anatomy (mid-medial third of the tubercle) as recommended by the manufacturer's surgical technique. Insert a single anterior or posterior pin (medially or laterally) into the trial tray to allow for internal / external rotational adjustment while maintaining optimal medial / lateral coverage.

Figure 2 - view of proximal tibia referencing the mid-medial third of tibial tubercle

Step 2: Sensor Insertion

Insert the VERASENSE Sensor with appropriate sized shim attached to replicate thickness of standard trial insert. In a tight knee capsule, it may be necessary to insert the VERASENSE Sensor prior to insertion of the femoral trial. DO NOT utilize excessive force or impact the sensor directly with a mallet.

Figure 3 - VERASENSE™ Sensor activated and inserted into knee

Step 3: Establish Tibial Tray Rotation Utilizing Contact Points

With the leg supported in 10° flexion, rotate the tibial tray to the most posterior contact point (internally or externally) as needed to horizontally align the medial and lateral contact points within 5° of each other. Reference protocol found in Appendix I on how to hold the leg using VERASENSE. A positive (+) value in the Contact Point Rotation (CP Rotation box) indicates internal rotation (IR); a negative (-) value indicates external rotation (ER). Figures 4-6.

When preferred tray rotation is achieved (within 5° Contact Point Rotation):

- Add additional Pin to stabilize tray
- Flex knee and confirm patellar tracking
- Record the final value

[figure not shown]

Figure 4 - VERASENSE™ Sensor as displayed on graphical user interface. CP (Contact Point) Rotation degree [in red box] references the degree of tibiofemoral incongruity. Yellow circles correspond to femoral contact points. The number 8 represents total pounds of pressure in the medial and lateral compartments

Figure 5 - Left: Medial and lateral femoral contact points (indicated by arrows) demonstrate tibiofemoral rotational incongruity, due to excessive IR of the tibial tray. Right: After correcting for IR, the femoral contact points demonstrate symmetry (indicated by arrows).

Figure 6 - Left: Example of excessive ER (indicated by arrows), as a result of referencing the mid-third of the tibial tubercle, shown by the sensor interface. Middle: Trial tibial/femoral components in place with the sensor; tibial tray visually and digitally exhibiting external rotation. Right: The tibial tray is rotated to improve congruity, as seen by the parallel contact points (indicated by arrows) on the sensor interface.

Step 4: Balance Soft-Tissue Sleeve

Once tibial tray rotation has been assessed, the medial and lateral compartment pressures will be evaluated in the coronal and sagittal planes. The soft tissue gaps will be evaluated and recorded at **10°**, **45°**, and **90°** of flexion, with the hip in neutral rotation and the femur supported just proximal of to the knee. The capsule must be closed provisionally during assessment at each pose using a towel clip placed above and below the patella in the medial retinaculum. Incremental balancing using a pie-crusting technique with an 18-gauge needle or #11blade scalpel is recommended to address ligamentous tension when necessary. Additional bony resections may be necessary for excessive loading (refer to surgical reference guide). Previous research evaluating the use of VERASENSE during TKA suggests a load differential of up to 15 lbs or less between the medial and lateral condyles is indicative of soft-tissue balance [7] (Figure 7). These balancing parameters will be the target in the sensor-guided group.

Figure 7 – Left: The mediolateral intercompartmental difference, pre-release, is 42 lbs. This value exceeds the 15 lb. limit, thus classifying this joint as “unbalanced.” **Right:** The mediolateral intercompartmental difference, post-release, is 1 lb. and was classified as “balanced” upon closing.

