2. STUDY DESIGN

The study is designed as a prospective, randomized (two-cohort) double-blinded clinical evaluation and will be conducted at multiple centers throughout the United States. Approximately 500 patients will be included and followed for a period of 2 years. Clinical Assessments will be performed at baseline, 6 weeks, 6 months, 1 and 2 years after surgery.

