The latest version of the KSS was developed in 2011 and introduced by the Knee Society. The latest version of the KSS originates from the popular KSS (from 1989); both physician and patient derived. It includes versions administered preoperatively and postoperatively. It has an initial assessment of demographic details, including an expanded Charnley functional classification. The objective knee score, completed by the surgeon, includes a VAS score of pain, walking on level ground and on stairs or inclines, as well as an assessment of alignment, ligament stability and ROM, along with deductions for flexion contracture or extension lag. Patients then record their satisfaction, functional activities, and expectations. Given the diverse activity profiles of many contemporary patients, the functional component of the score was improved to include a patient-specific survey, which evaluates features such as standard activities of daily living, patient-specific sports and recreational activities, patient satisfaction, and patient expectations. The new Knee Society Knee Scoring System has been developed and validated, in part, to better characterize the expectations, satisfaction, and physical activities of the younger and more diverse population of current patients undergoing TKA. The score was validated in a thoughtful and methodical fashion confirming internal reliability and analyzed for differential item functioning. The new Knee Society Scoring System is broadly applicable across sex, age, activity level, and implant type. Completing the questionnaire takes 10 to 30 minutes.
- **Forgotten Joint Score (FJS)**
The FJS is a patient reported outcome measure, consisting of 12 questions (e.g. awareness traveling in a car or climbing stairs?). It uses a 5-point Likert response format and the raw score is transformed to range from 0-100 points. High score indicates good outcome, e.g. a high degree of forgetting the joint in everyday life (forgotten joint phenomenon). The FJS has a low ceiling effect and was designed to discriminate between good, very good and excellent outcomes after TKA.
- **Knee Pain Evaluation Form**
The knee pain evaluation will be used to assess the prevalence and location site of knee pain when applicable. This evaluation will be completed by the investigator post total knee surgery during the intervals defined in Table 1 “Schedule of study assessments”.

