Each patient who signs an informed consent document will be given a unique, sequential 3-digit number. The three initials of each patient will be used (first, middle, last). In the case where the subject does not have a middle initial, that placeholder will be held by a dashed line (-). This unique patient identifier will be used on all study-related documentation for each subject enrolled in the study. The patient's initials will be used to further identify the subject; no names will be used.

13. Screening Enrollment Logs

A record of all patients consented for the study, with their consecutively assigned study numbers, will be maintained in the site's Regulatory Binder. This log will be identified as the Screening/Enrollment Log. Patients who sign a consent form but who do not continue into the study for whatever reason (i.e., cancel surgery) will be assigned a unique subject identifier which **WILL NOT BE REASSIGNED** to anyone else.

14. Patient Identification

Each patient who signs an informed consent document will be given a unique, sequential 3-digit number. The three initials of each patient will be used (first, middle, last). In the case where the subject does not have a middle initial, that placeholder will be held by a dashed line (-). This unique patient identifier will be used on all study-related documentation for each subject enrolled in the study. The patient's initials will be used to further identify the subject; no names will be used.

Example: Subject number: 001.

Subject initials: FML where F = first initial, M = middle initial, L = last initial. This subject's unique identifier would be 001 and uniquely associated with the initials FML.

15. Institutional Review Board Approval and the Informed Consent Document.

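### Does calling each group a consecutive series, with no allocation method described, mean the trial may not be randomized?

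*Combined protocol and SAP*

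**What the plan says.** Section 2 describes a "prospective, randomized (two-cohort) double-blinded clinical evaluation" of about 500 patients. Section 5 says "Patients will be enrolled in a consecutive series consisting of two cohorts (Groups A and B") and then defines Group A and Group B, in the same words, as 250 "consecutive patients who will undergo primary unilateral PCL-retaining" or PCL-sacrificing surgery, without or with sensor guidance.

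Three further statements bear on allocation:

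- Section 5, on blinding: "The investigator will be blinded to the patient study number and the patient will be blinded to his/her assigned group".
- Section 5, on consent: patients are told that "they may or may not receive their knee replacement procedure using the VERASENSE Knee System".
- Section 7: each centre is expected to enrol about 100 patients, 50 per group.

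On the study number, Sections 12 and 14 say: "Each patient who signs an informed consent document will be given a unique, sequential 3-digit number". They add: "This unique patient identifier will be used on all study-related documentation for each subject enrolled in the study". Section 13 places the log of these numbers in the site's Regulatory Binder. No section available to this check gives a sequence, blocks or strata, a concealment method, a time of assignment or a responsible person. A few pages of the document were not available.

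**The concern.** A trial that claims randomization normally says how it is done. Here the section a site would consult has no allocation step, and the word *consecutive* is attached to each group separately. Taken literally, that permits filling one group and then the other. Group would then be confounded with calendar time and with each surgeon's accumulated cases, and the ANOVA and t-tests in Section 10 name no term for either. Section 3 also lists a learning curve among the secondary objectives, which draws attention to case order.

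The one sentence that might be about concealment is hard to interpret. It blinds the investigator to the study number, yet that number is sequential, appears on all study documentation and is logged at the site. The investigator also fills in the Knee Pain Evaluation Form (Section 9: "This evaluation will be completed by the investigator post total knee surgery"). If the surgeon who enrols could foresee the next assignment, patients could be steered between groups even in a concurrent design, and no later analysis would reliably undo that.

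**Working it through.** **Counts (Sections 2, 5 and 7).** 250 + 250 = 500. 500/100 implies 5 centres, and 5 × 50 = 250 per group. The figures agree with one another. They fit concurrent 1:1 assignment and 50-then-50 cohorts equally well, so counts alone do not settle the matter.

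**Reading the passages together.**

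| Statement | Concurrent randomization | One cohort after the other |
|---|---|---|
| Randomized (Section 2) | fits | contradicts |
| Double-blinded; patient blinded to an assigned group (Sections 2, 5) | fits | strained |
| Consent: sensor may or may not be used (Section 5) | fits | strained |
| One consecutive series made up of both groups (Section 5) | fits | possible |
| 50 per group per centre (Section 7) | fits | fits |
| 250 consecutive patients in each group (Section 5) | fits if it means unselected patients | fits literally |

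Only the last row suggests sequential cohorts, and it has an ordinary meaning (patients taken as they present) that agrees with every other row.

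**What the sequential reading would cost.** These figures are conditional. Assumptions not in the documents: 50 of one group then 50 of the other at each of 5 centres, two-sided 5% level, 80% power, all 250 per group analysed.

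- Unadjusted standard error: √(2/250) = 0.0894 SD. Detectable difference: (1.960 + 0.842) × 0.0894 = 0.25 SD.
- Variance inflation from adjustment is 1/(1 − R²), where R² comes from regressing group on the other terms. For linear case order with centre, R² = 0.75, so the factor is 1/0.25 = 4.00. Effective sample size is 500/4 = 125, and the detectable difference is 0.25 × √4 = 0.50 SD.
- Cubic trend in case order: factor 7.12, effective size 500/7.12 = 70, detectable difference 0.67 SD.
- Calendar time used instead of case order: 3.38, 2.48 and 3.23 if time grows as the square, cube or square root of order. With five centres accruing at random and different rates (assumed multipliers 0.5 to 2), the mean is about 3, and the factor is below 4 in more than 99% of 2,000 runs. Fourfold is therefore not a general minimum.
- Concurrent permuted blocks of 4 and 6 within centre: factor 1.00.

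**What drift would do if left unadjusted.** With one group wholly first and a linear drift D in the outcome over accrual, the group means sit at D/4 and 3D/4, so the bias is D/2. For D = 0.2 SD, bias/SE = 0.10/0.0894 = 1.118, and the type I error is Φ(1.118 − 1.960) + Φ(−1.118 − 1.960) = 0.20. For D = 0.1, 0.3 and 0.4 SD it is 0.09, 0.39 and 0.61. The documents give no D, so these show sensitivity only.

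**The case for a change.** The strongest case for a change is that intent is not a procedure. Phrases that imply randomization do not tell a site what to do or let a reader verify what was done. If allocation were faulty, nothing could restore it after surgery, and writing the method down costs a few sentences and no patients. The sentence on the study number is unclear whatever was intended.

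Much of this stands. The method is not described, and concealment from the enrolling surgeon cannot be judged from this text. Three things limit what follows from it:

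- Missing description is not faulty allocation. If patients were properly randomized, reporting the method is the whole remedy.
- The study-number sentence is unexplained rather than shown to fail. Nothing says that the number reveals the group, or that the investigator assigns the numbers or keeps the log.
- The learning-curve objective adds little. Section 3 speaks of *any* such curve, and one specific to the sensor would fall in Group B under either design. Section 6 also specifies experienced, high-volume surgeons, which may limit general drift.

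The choice of strata, block sizes and their variation is a choice among several valid schemes. Fixed blocks would leave 33% (size 4) or 25% (size 6) of assignments certain to someone who knows the earlier ones, but the documents do not say that such blocks are used.

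**Conclusion.** The gap is one of description, and no change to the plan is required. A sponsor following the document as a whole would enrol unselected eligible patients and randomize them 1:1 within centre, which supports the planned comparison. The text is ambiguous, not contradictory, and the size of any bias cannot be stated. The fourfold variance figure applies only to linear case order under an assumed 50-then-50 layout and should not be quoted as a property of this trial.

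This conclusion rests on reading *consecutive* as unselected and on allocation having been carried out as the design label says. It would change if site records showed one group enrolled before the other, or assignments visible to surgeons before enrolment. The comparison would then have to be treated as non-randomized or open to selection.

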3. OBJECTIVES

The objectives of the study are twofold: 1) Evaluate how intra-operative sensing may assist the surgeon with tibiofemoral rotational alignment by testing the precision and variability of setting tray rotation to the mid-third of the tibial tubercle. 2) Understand if patients with a combined axial rotation couple at the tibiofemoral joint and quantitative intercompartmental balance, achieved with the use of VERASENSE, exhibit less post-operative knee pain and improved clinical outcomes. Radiographic outcomes will also be assessed to measure post-operative alignment and to evaluate the prevalence and location of radiolucency and/or osteolysis.

Hypothesis: TKA with VERASENSE results in a more reliable and precise option for establishing implant-to-implant congruency and joint balance leading to less knee pain, faster return to normal activities and higher patient satisfaction compared to TKA without VERASENSE.

The secondary objectives of the study are to establish correlations between the intraoperative VERASENSE data, the surgeon's perception of balance and patient outcomes in addition to understanding any learning curve associated with using new technology.

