9. DATA COLLECTION

All data collection will be prospective and will be collected after the patient has voluntarily agreed to participate in the study by signing and dating an IRB-approved informed Consent and HIPAA document (as required by the local IRB). Data will be collected according to the scheme outlined in Table 1.

a. **Methods:**

- i. Data can be collected via paper form, or entered directly to an online database, if applicable.
- ii. If the site has an existing database, data may be sent to OrthoSensor via raw data format in an excel spreadsheet. If using a local database, it must be ensured that the data in the spreadsheet is compliant with the methods presented in the case report forms, as all data must be available for statistical analysis.

b. **Data and Clinical Assessments:**

- Patient Demographics: Age at surgery, gender, surgical side, height, weight, primary diagnosis. This data is collected from the medical record.
- Operative Data: Part Numbers (if able) or Femoral Component Type & size, Tibial Tray Type & Size, Tibial Bearing Type & Size, Patella Type & Size, OR Time, Surgical Technique, Surgical Approach, Operative Complications, Length of stay. This data is collected from the medical record.
- Length of stay, Discharge Destination: Based on the operation day and day of discharge, the length of hospital stay is determined.
- Patient Reported Outcome Measures – Perceived functioning, including pain, satisfaction and function will be measured using three patient reported outcome measures (PROMs).

- **EQ-5D**
A standardized instrument for use as a measure of health outcome
- **Knee Society Score (2011 Version)**

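### The two arms' rotation readings are not like for like: Group B's only instructed value is taken unblinded, at the 5° target and before balancing, while Group A's is blinded and pre-closure

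*Combined protocol and SAP*

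**What the plan says.** **Objective.** Section 3 sets Objective 1 as "testing the precision and variability of setting tray rotation to the mid-third of the tibial tubercle". The hypothesis in the same section is between groups: surgery with the sensor is expected to be more reliable and precise than surgery without it.

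**Control arm (Group A).** Section 5 places this arm's reading ahead of closure, in these words: "closing the arthrotomy, VERASENSE will be utilized in a surgeon-blinded fashion to record rotational alignment and intercompartmental pressures through a range of motion".

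**Sensor-guided arm (Group B).** In Step 3 of the surgical protocol (Section 5), the surgeon watches the display with the leg at 10° flexion and turns the tray until the contact points agree within 5°. The instruction to record a final value is listed under "When preferred tray rotation is achieved (within 5° Contact Point Rotation", after adding a second pin and checking patellar tracking. Step 4 follows. Its recording instruction, "The soft tissue gaps will be evaluated and recorded at", covers three flexion angles (10°, 45° and 90°) and does not mention rotation. Step 4 also permits further surgery. Pie-crusting "is recommended to address ligamentous tension when necessary", and the same step allows for recutting bone: "Additional bony resections may be necessary for excessive loading".

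**Data and analysis.** Section 4.2 shows that the software can output rotation ("kinematic tracking; tray rotation, tibia varus/valgus axis; mechanical axis"). The operative data listed in Section 9 run from component details to "OR Time, Surgical Technique, Surgical Approach, Operative Complications, Length of stay" and include no sensor reading for either arm. Section 10 plans ANOVA and t-tests. It names no rotation variable and no method for comparing variability. The radiographs in Section 9 are anteroposterior and mediolateral, with no axial imaging named.

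**The concern.** A precision comparison needs the same quantity, measured the same way, at the same stage in both arms. Here the written readings differ in four respects: stage of surgery, knee position, whether the surgeon sees the display, and whether the value is conditional on meeting a target.

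The last matters most. Group B's value is the number the surgeon adjusted until it met the 5° criterion, so it records that the step was completed. Group A's value describes the knee shortly before closure. Being within 5° is partly what the device is meant to achieve. But the recorded value cannot separate a knee that is still within 5° at closure from one that was within 5° only when the tray was pinned.

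What is at stake is the rotation half of the hypothesis. Patient-reported outcomes are untouched. So is a t-test on signed mean rotation if errors are symmetric, although such a test does not address precision.

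**Working it through.** **1. The readings side by side**

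| Feature | Group A (Section 5) | Group B (Step 3) |
|---|---|---|
| Stage | Before arthrotomy closure | Before Step 4 balancing |
| Display | Hidden from surgeon | Guides surgeon |
| Knee position | Range of motion | 10° flexion |
| Condition for recording | None | Within 5° |

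The plan has no rotation figure to reproduce: it gives no SD, effect size, alpha or power. The only input below taken from the documents is 250 knees per arm. The rest is assumed, and all results are illustrative.

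**2. Share within 5° (no drift model needed)**

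Assume every Group B knee complies, so Group B is recorded as 250/250. Two-sided Fisher's exact test:
- against 245/250 in Group A (5 outside): p=0.061
- against 244/250 (6 outside, 6/250 = 2.4%): p=0.030

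Group B is therefore declared better whenever Group A has 244 or fewer within 5°. If both arms truly share the same proportion π at closure, the chance of that is P(X ≤ 244), with X ~ Binomial(250, π):

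| Assumed π | 99% | 98% | 97% | 96% |
|---|---|---|---|---|
| Group B declared better | 4.1% | 38.4% | 76.3% | 93.7% |

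**3. The same measure when the sensor truly helps**

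Assume Group A rotation is N(0°, SD 6°). Its share within 5° is 2Φ(5/6) − 1 = 59.53%, so the recorded gap is 100 − 59.5 = 40.5 points.

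Assume Group B is uniform within ±5° at Step 3 and then drifts by independent N(0, s). Its share at closure is 1 − 0.2·s/√(2π):

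| Drift SD s | 1° | 2° | 3° |
|---|---|---|---|
| Share, all knees drift | 92.0% | 84.0% | 76.1% |
| True gap (points) | 32.5 | 24.5 | 16.5 |
| Share, a quarter drift (0.75 + 0.25 × row 1) | 98.0% | 96.0% | 94.0% |
| True gap (points) | 38.5 | 36.5 | 34.5 |

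Even in the worst cell (59.5% v 76.1%), a correctly timed reading would favour Group B in about 97% of trials. The gap is overstated; the verdict rarely changes.

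**4. Spread**

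Brown-Forsythe test, two-sided 5%, 250 per arm, 10,000 simulated trials per cell. The arms are identical at closure. Group B's recorded value is uniform on ±5°. Group A has the same distribution with a fraction of knees changed. Cells show the percentage of trials favouring B / favouring A.

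| Change after Step 3 | s=1° | s=2° | s=3° |
|---|---|---|---|
| Noise, all knees | 10.5 / 0.4 | 72.8 / 0 | 99.9 / 0 |
| Noise, half | 4.9 / 0.9 | 27.8 / 0 | 79.0 / 0 |
| Noise, a quarter | 3.8 / 1.6 | 10.1 / 0.3 | 30.7 / 0 |
| 20% shrinkage plus noise, all knees | 0 / 83.6 | 2.2 / 3.1 | 90.7 / 0 |

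With no drift the test rejects in 4.7% of trials. With matched readings it rejects in 4.2–5.4% across the noise and shrinkage settings tried. The signed-mean t-test stays at about 4–6% throughout.

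The sign of the bias depends on an assumption the documents cannot settle. Unrelated drift flatters Group B, corrective drift penalises it, and no drift leaves no timing bias.

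**The case against.** **The plan names neither endpoint used above.** This stands. In the plan 5° is a surgical target, and Section 10 offers only ANOVA and t-tests. But Section 10 names no rotation endpoint at all, and Objective 1 asks about variability, so some such analysis would have to be chosen later, from readings that do not match.

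**The tray is pinned before the value is recorded.** This stands as a reason to doubt large drift in the tray itself. Contact-point rotation, however, is derived from where the femur bears. Appendix II includes ligament releases prompted by contact-point position, and recutting the tibial plateau. Change is possible, but its frequency, size and direction are not given.

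**Objective 1 may be a within-knee test.** Its wording can describe setting the tray to the tubercle and seeing how far the sensor disagrees. That is a fair reading. The between-arm comparison comes from the hypothesis. The within-knee reading would need Group B's value before adjustment, which the text does not ask for either.

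**A later or matching value may exist.** The case report forms were not supplied, the sensor is in place during Step 4, and Group A's range of motion may include 10°. All true, and a reader should not infer that no later Group B value will be captured. The supplied text simply does not require or name one.

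**Group B may not reach 100%.** Correct. The plan does not say what is recorded for knees that miss 5°, so 250/250 describes full compliance only.

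**The equal-arms case is implausible.** The introduction expects landmark referencing to be variable, so 96–99% within 5° in Group A runs against the plan's premise. This is why part 3 of the working sits beside part 2.

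**Conclusion.** The concern holds in limited form. Followed as written, the plan gives a blinded, pre-closure rotation reading in Group A and an unblinded, target-conditioned, pre-balancing reading in Group B. Comparing them would not be a like-for-like test of precision.

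The direction is fixed for one summary only. Among compliant knees the recorded share within 5° can equal or exceed, but not fall below, Group B's share at closure. For spread or absolute deviation, neither size nor direction is known.

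A reader might infer that the trial is bound to show a spurious precision advantage for the sensor. The documents do not support that: they do not say whether contact-point rotation changes after Step 3, and they commit to no rotation test. Nor do they support the view that the sensor's benefit would vanish under a matched reading. Where Group A's true share is well below Group B's, mainly the size of the gap changes.

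Every magnitude here rests on assumed compliance, drift or SD. This is an inexpensive improvement worth making, held with medium confidence.

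**What to change.** - **Reading.** In both arms, save one rotation reading after all balancing is complete and before the arthrotomy is closed, at the same stated knee position or positions and with the same provisional capsule closure. In Group B, take it as a research reading, with the display hidden for that reading only, once sensor-guided work has finished. Guidance is then unaltered.
- **Analysis.** Name this reading in Section 10 as the compared rotation variable. State the knee position analysed and specify a test of spread or absolute deviation. Include all randomised knees, among them those that missed the 5° target.
- **Step 3 value.** Keep it as a record of compliance, and say what is entered when 5° is not reached.
- **Objective 1.** State whether it is between arms, within knee, or both.
- **Limitation.** Acknowledge that the sensor is both Group B's target and the yardstick for both arms. Matched timing does not cure this.

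**Cost.** A little theatre time with a sensor already in use, a standardised position and capsule closure for Group A's existing reading, one case report form field, and a few sentences in Section 10. The rotation result may be less favourable to the device. A reading not taken before closure cannot be recovered later.
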